4. STUDY INFORMATION

The location of the research will take place on scheduled dates at the Loma Linda University School of Allied Health Professions campus, [name], Loma Linda, California and Stanbridge University campus on [name] in Irvine, California.

Expected start date is December 1, 2017 and expected end date of research is December 1,

2018. The research consists of a mixed method design and includes a single blind

randomized control trial with a repeated measure design. A qualitative element includes semi-structured interviews of participants.

5. INCLUSION/EXCLUSION CRITERIA

INCLUSION

- Adults > 18 years of age
- Fluent in English
- Report signs and symptoms of carpal tunnel syndrome
- Pain, numbness, and tingling of the forearm, wrist, or hand, which worsen at night
- Demonstrate positive Phalen's Test or Tinel's Test of the affected extremity

EXCLUSION

- Currently receiving treatment for carpal tunnel syndrome
- History of surgical carpal tunnel release
- Pregnant
- Diabetes not controlled by medication
- Radiculopathy ie: cervical radiculopathy, diabetic radiculopathy
- Thoracic outlet syndrome
- Allergy to adhesives or compromised skin integrity
- Past history of traumatic event, surgery, or congenital impairment of the forearm, wrist, or hand

6. SUBJECT RECRUITMENT & SCREENING

Based on a power analysis, 64 participants are needed with an expected attrition rate of 20% increasing the total number of participants to 78, with 26 in each of three groups.

Participants will be fluent in English, males and females age 18 years and older. The study will include participants from any race or ethnicity that meet eligibility criteria and demonstrate a positive Phalen's Test or positive Tinel's Test. The study population includes individuals who have symptoms of or have received a diagnosis of carpal tunnel syndrome, or experience forearm wrist hand pain and currently not receiving treatment. If participant has symptoms in both extremities, the researcher will use each extremity as a separate unit and apply corresponding intervention to both extremities.

Participants will be recruited using snowballing and judgmental sampling via word-of-mouth, flyers, emails, and social media with a \$5.00 gift card provided per visit for each of the five visits for the study. Flyers will be distributed throughout the Southern California area due to proximity but participants may come from any region if satisfying inclusion criteria and time commitment. Flyers will be placed in, but not limited to, common public places such as pet grooming places, community postings, manufacturing facilities, clinics, hair stylists, dental hygienists, sonographers, office buildings, and more. The principal investigator or appropriate personnel for Loma Linda University, and by the student researcher or appropriate personnel for the Stanbridge University access will acquire email addresses of potential participants. Specific social media outlets will include posting on but not limited to, Facebook, Instagram, and Twitter, with a website that will be accessed at: carpaltunnelstudy.wordpress.com for information. The contact information of the principal

investigator and student researcher will be available on the flyer with an invitation to contact researchers with any questions about the study.

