The primary purpose of this randomized controlled trial graduate student research study is to explore the effect of dorsal application of Kinesio Tape on occupational performance as measured by pain, strength, and function of individuals with carpal tunnel syndrome forearm wrist hand pain as compared to the usual and accepted most common non-surgical intervention of lumbrical stretching exercises and general cockup splint. The secondary purpose is to explore changes in occupational performance through semi-structured interviews in order to understand if Kinesio Tape contributed to results and if so, how. In order to help us understand how the participants perceived the interventions, the third purpose is to explore concepts of adherence to interventions with carpal tunnel syndrome.

b. Objectives

1. Determine if the dorsal application of Kinesio Tape applied to the wrist extensors for individuals with carpal tunnel syndrome and forearm wrist hand pain makes a difference in occupational performance as measured by pain, strength, and function.
2. Explore the perspectives of participants to understand if Kinesio Tape contributed to changes in occupational performance, and if so, how.

3. Explore concepts of adherence to interventions with carpal tunnel syndrome.

c. Procedures involved (Research Interventions)

The following procedures will be used for this multi-method study design that consists of a randomized control trial and descriptive qualitative study, upon IRB approval:

1. Recruit via snowballing, word-of-mouth, flyers, emails, and social media (See Appendix A)
2. Respond to study interest via Phone Script to answer questions regarding the study (See Appendix B) and set up a meeting time to review consent and initiate study procedures.
3. Review Informed Consent, HIPPA documents, and Patient's Bill of Rights and obtain consent from those interested in participating in study.
4. Screen participants for inclusion criteria by administering the Phalen's Test or Tinel's Test (Appendix C).
5. Administer Demographic questionnaire (Appendix D).
6. Administer baseline Week One Visit One Boston Carpal Tunnel Questionnaire, Numeric Pain Rating Scale, Visual Analogue Scale (Appendices E – F - G). If participant has symptoms in both extremities, the researcher will use each extremity as a separate unit and apply corresponding intervention to both extremities.
7. Collect Week One Visit One Baseline Grip and Pinch measurements (Appendix H).

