8. Randomly assign participants using a random number generator, to one of three groups:
Intervention group, control group, or usual protocol group. A script will be used to control for bias and ensure consistency between groups.

Intervention group:

The student researcher and/or student research assistants who have been trained in Kinesio Tape and application procedures will apply the baseline dorsal application of Kinesio Tape according to determined protocol. The Kinesio Tape will be measured along the participant's lateral epicondyle to metacarpophalanges, the Kinesio Tape then bifurcated. Anchor Kinesio Tape on the dorsal side at the musculotendinous juncture to digits 1 and 5, just past the carpalmetacarpophalangeal joint of digit 1 and metacarpophalange of joint 5, wrist in flexion to stretch the skin, paper off tension (10%). Kinesio Tape application to digits 1 and 5 with carpalmetacarpophalangeal and metacarpophalange flexion during application. Two space correction pieces

applied to both the extensor and flexor surface at 75% stretch, then radially deviate, smooth edges, ulnarly deviate, smooth edges, repeat.

A handout with Kinesio Tape Removal Instructions will be provided (Appendix I). A symptom journal will be provided with instructions to complete daily (Appendix J). A script will be used with participants (Appendix K).

Control group:

The student researcher and/or student research assistants will apply the Sham application of Kinesio Tape, a four-inch strip of Kinesio Tape to the participants' shoulder (scapular spine). A handout with Kinesio Tape Removal Instructions will be provided (Appendix I). A symptom journal will be provided with instructions to complete daily (Appendix J). A script will be used with participants (Appendix K).

Usual protocol group:

The student researcher and/or student research assistants will provide a general wrist cock up splint with instructions to wear nightly and record compliance in a Splint and Exercise journal (Appendix L). Wrist Lumbrical exercises will be demonstrated by the student researcher or student research assistants and a handout with instructions provided (Appendix M). A symptom journal will be provided with instructions to complete daily (Appendix J). A script will be used with participants (Appendix K).

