9. DATA COLLECTION

Data collection procedures on the affected extremity include psychometric assessments of pain, using the Numeric Pain Rating Scale and Visual Analogue Scale. Occupational performance will be measured using the Boston Carpal Tunnel Questionnaire completed by the participants and grip and pinch from each participant will be recorded by the student research assistants.

At the final visit, the student researcher and/or student research assistants will conduct a 30-minute 6-item semi-structured interview exploring the intervention group participant's perception of wearing Kinesio tape and its impact on the participant's occupational performance.

Study intervention will be held at the beginning of the week and the end of the week during various times of day to account for sign and symptoms related to occupation and activities of daily living. The researchers know which intervention is being studied; however, the participants will not know which intervention is being studied to increase accuracy of findings. The benefit of blinding participants in this graduate student randomized controlled trial to the objective of the study is to determine if there is indeed a benefit of the intervention of dorsal application of Kinesio Tape versus the usual protocol or current care of splint and lumbrical exercises for carpal tunnel syndrome forearm wrist hand pain. There Kinesio Tape application on the shoulder is to determine if there is an intervention effect is evidence to suggest even that application site could be beneficial. All participants will be emailed the results of the study.

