11. DATA ANALYSIS

The research analysis plan will include a repeated measures multi-factorial analysis of variance to analyze continuous data for the functional grip and pinch measurements, with an analysis of covariance to rule out any confounding variables between groups. For Objective 1 of the randomized controlled trial of the study continuous data will be analyzed with change score analysis from baseline to end of study. To compare groups post-hoc Bonferroni will be used. Non-parametric statistics using the Friedman's Test will be used with the Numeric Pain Rating Scale, Visual Analogue Scale, and Boston Carpal Tunnel Questionnaire.

For Objective 2, qualitative data will be analyzed for thematic coding. Transcripts will be individually read and coded for emerging themes by the research team and then analyzed as a group to increase rigor. For Objective 3 to explore concepts of adherence to interventions with carpal tunnel syndrome, triangulation will be used with data obtained through interviews and with journals using a deductive approach to explore Kinesio Tape on performance. Data will be analyzed until redundancy is achieved.

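### The primary purpose is dorsal tape versus usual protocol, but the 64 is not tied to that contrast and the analysis tests it only post hoc; it should be the planned primary contrast at 5%

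*Combined protocol and SAP*

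**What the plan says.** Section 6 (Subject Recruitment & Screening) gives the size as one total: "Based on a power analysis, 64 participants are needed with an expected attrition rate of 20% increasing the total number of participants to 78". Allocation is equal, at 26 per arm. The section names no endpoint, test, contrast, alpha, power, effect size or SD.

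Section 8 (Study Design), part a, states the primary purpose as the effect of dorsal tape on pain, strength and function "as compared to the usual and accepted most common non-surgical intervention of lumbrical stretching exercises and general cockup splint". Section 9 (Data Collection) repeats the contrast when it explains the blinding: "dorsal application of Kinesio Tape versus the usual protocol or current care of splint and lumbrical exercises". Objective 1, in section 8 part b, names no comparator.

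Section 8, part c, step 8 randomises to "Intervention group, control group, or usual protocol group"; the control is sham tape on the shoulder.

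Section 11 (Data Analysis) plans a repeated-measures ANOVA with ANCOVA for grip and pinch, and change scores for the continuous data under Objective 1. On group comparisons it says only: "To compare groups post-hoc Bonferroni will be used". The two pain scales and the Boston questionnaire go to Friedman's test.

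**The concern.** The stated question is a comparison of two arms. The stated size is a total over three, and the planned inference is an overall analysis followed by pairwise tests of equal standing. An overall test among three arms can be significant only because sham does worse, which does not answer whether tape differs from the usual protocol. The contrast that does answer it uses two thirds of the participants and, as planned, pays a multiplicity penalty shared with comparisons that the primary purpose does not ask for.

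Two things are at stake. Saying that 64 are needed suggests that this number is adequate for the primary purpose, which the document does not show. The post-hoc status of the key contrast also costs precision that pre-specification would recover at no cost in recruitment.

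**Working it through.** **Inputs from the document.** Needed: 64 in total. Enrolled: 78, or 26 per arm. Attrition: 20%. Arms: three. Pairwise adjustment: Bonferroni.

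**Assumed, because not stated.** Two-sided 5% overall; 80% power; three pairwise comparisons, so 0.05/3 = 0.0167 each; Cohen's f = 0.40 for the overall-test reading.

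**1. Numbers per arm.** 64/3 = 21.3. After attrition, 26 × 0.8 = 20.8, or 62.4 in all. Both are about 21.

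**2. Can 64 be reproduced?** Not from stated inputs, since there are none. Candidates:
- Three-group F test, df 2 and N − 3, noncentrality N × f², f = 0.40, alpha 0.05: N = 63 gives 79.8% and N = 64 gives 80.5%. So 64 is the smallest total reaching 80%.
- Repeated-measures between-arm F test over five visits, noncentrality N × f² × 5/(1 + 4ρ): f = 0.40 with ρ = 0.7 gives 64 at 90% power; f = 0.33 with ρ = 0.6 gives 64 at 80%.
- Two-sample t test at d = 0.5: 64 per arm. Two arms of 32: 80% power at d = 0.71.

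The first matches, but it is not the only setting that does.

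**3. Tape versus usual protocol if the first candidate is the basis.** For f = 0.40 the pairwise standardised difference d depends on the pattern of means:
- Tape and usual adjacent in three evenly spaced means: d = f√6/2 = 0.490
- Only tape differs: d = 3f/√2 = 0.849
- Tape and usual at the extremes, sham between: d = f√6 = 0.980

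Power from the noncentral t with noncentrality d√(n/2), n = 64/3, pooled error df = 61:

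| Pattern | d | Bonferroni (1.67%) | 5% |
|---|---|---|---|
| Adjacent | 0.490 | 20% | 35% |
| Only tape differs | 0.849 | 62% | 78% |
| Extremes | 0.980 | 77% | 88% |

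If only sham differs, d = 0: the overall test can reject with no tape-versus-usual difference at all.

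**4. Sensitivity to the basis.** Under the five-visit setting with f = 0.40, ρ = 0.7 and 90% power, the effective f is 0.40 × √(5/3.8) = 0.459. The Bonferroni figures become 27%, 76% and 88%.

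**5. Detectable difference, which does not depend on where 64 came from.** With n = 20.8 per arm, error df = 59.4 and 80% power: d = 1.03 at 1.67% and d = 0.88 at 5%. The 95% confidence interval for the contrast has half-width 2.00 × √(2/20.8) = 0.62. The unit is the SD of the outcome as analysed. If the baseline-to-final correlation were 0.5, 1.03 residual SD under ANCOVA would be 1.03 × √(1 − 0.25) = 0.89 raw SD; at 0.8 it would be 1.03 × √(1 − 0.64) = 0.62 raw SD. Both correlations are illustrations.

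**The case against.** The strongest reply is that the origin of the 64 is unknown, so any power figure for the key contrast is conditional. That stands. A reader might infer that the 64 was computed for an overall test, or that tape versus usual protocol has power of only 20% to 62%. The documents support neither. No test is named, other settings give the same total, and that range leaves out the pattern with tape and usual at the extremes (77%) and the unadjusted figures (35% to 88%).

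Three further points stand in part. First, the t-based figures describe grip and pinch only; pain and the Boston questionnaire go to Friedman's test, so the figures cannot be read across to them. Second, baseline adjustment, repeated measures and counting each hand as a unit all change the power, and the document gives no correlations from which to say by how much. Third, Objective 1 names no comparator, and section 9 gives the sham arm a purpose of its own, so an overall three-arm test is not foreign to the trial. This is a reason to keep the sham comparisons as secondary. It is not a reason to leave the contrast named in the primary purpose without a planned test.

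A reader might also infer that the plan would take a non-significant result as equivalence. Nothing in it says so. Reporting the confidence interval is enough to guard against that.

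**Conclusion.** The concern holds in a limited form. The primary purpose names tape versus usual protocol; the 64 is a three-arm total with no stated link to it; and section 11 tests that contrast only as one of several post-hoc comparisons. This mismatch can be read directly from the text and needs no assumption.

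The size of the effect on power does need assumptions. If 64 came from an overall F test at f = 0.40, all three patterns of means fall below 80% under Bonferroni over three comparisons (20%, 62%, 77%), and one of the three exceeds 80% at an unadjusted 5%. Under another setting that also gives 64, one pattern exceeds 80% even with Bonferroni (88%). A flat statement that the trial is underpowered for its primary question would therefore go too far.

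The firmer figure is the gain from planning the contrast: at about 21 completers per arm, the detectable difference falls from about 1.03 to 0.88 SD. Since (1.028/0.883)² = 1.36, this is roughly what 36% more participants would buy at the Bonferroni level. It rests on three comparisons, independent participants, 20% attrition, 80% power and a normally distributed outcome.

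**What to change.** **Section 11.** Name dorsal tape versus usual protocol as the single planned primary contrast for the continuous outcomes, grip and pinch. Test it at two-sided 5% and report it with its confidence interval. Treat the comparisons involving sham as secondary; whether to test tape versus sham in a fixed order after the primary contrast is a choice for the sponsor.

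**Section 6.** Do not present 64 as sufficient for the primary purpose. State what the design can detect, as an illustration for grip and pinch only. For example: with about 21 completers per arm, there is 80% power at two-sided 5% for a tape-versus-usual difference of about 0.88 SD of the analysed outcome (residual or change-score SD, not raw SD). Say that this figure does not apply to the outcomes sent to Friedman's test. If the inputs behind the 64 are on file, add them.

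**Cost.** Wording in two sections and no extra participants. The stated sensitivity looks less favourable, and the sham comparisons become secondary.

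### Enrolling 78 does not cover 20% attrition: about 62 participants would remain, not the 64 said to be needed

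*Combined protocol and SAP*

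**What the plan says.** The sample size is set out in one sentence of section 6 (Subject Recruitment & Screening), which states that "64 participants are needed with an expected attrition rate of 20% increasing the total number of participants to 78". It contains four figures:

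- the number required: "Based on a power analysis, 64 participants are needed";
- the assumed loss, 20%, given as an expected attrition rate;
- the enrolment target: "increasing the total number of participants to 78";
- the allocation: "with 26 in each of three groups".

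The sentence does not show how 64 was inflated to 78. It also does not give the alpha, power, effect size, endpoint or test behind the 64. No other section gives a different sample size or attrition rate. Section 11 (Data Analysis) mentions neither, and describes no method for missing data.

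**The concern.** The purpose of an attrition allowance is that, after the expected loss, the number required by the power analysis remains. The plan presents 78 as the figure that achieves this for 64 at 20% loss. A 20% loss from 78 is 15.6 people, whereas 78 exceeds 64 by only 14, so the allowance is smaller than the loss it is meant to absorb.

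At stake is whether the enrolment target delivers the number the plan itself says it needs. If it does not, expected power is below whatever level was planned, and a reader who relies on the sentence is misinformed about how much loss the trial can bear. This is the only sample-size statement in the document, so nothing elsewhere corrects it.

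**Working it through.** **Inputs**, all from section 6: required number 64; attrition 20%; enrolment target 78; three groups of 26. The 64 is taken as given, because the inputs behind it are not stated and it cannot be re-derived.

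**Reproducing the plan's figure.** Inflating by multiplication:

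- 64 × (1 + 0.20) = 76.8
- 76.8 / 3 = 25.6 per group, rounded up to 26
- 26 × 3 = 78

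This matches the stated total and group size exactly. The plan gives no formula, so this route is inferred.

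**Checking what 78 delivers.** Completers = enrolled × (1 − attrition):

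- total: 78 × 0.80 = 62.4, against 64 required, a shortfall of 1.6
- per group: 26 × 0.80 = 20.8, against 64/3 = 21.3, a shortfall of about 0.5

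**Largest attrition that 78 can bear while keeping 64.** 1 − 64/78 = 0.179, or 17.9%.

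**Correct inflation.** Enrolled = required / (1 − attrition):

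- 64 / 0.80 = 80
- 80 / 3 = 26.7 per group, rounded up to 27, so 27 × 3 = 81
- check: 80 × 0.80 = 64.0 and 81 × 0.80 = 64.8, both at least 64

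**What the shortfall costs in power (illustration).** This rests on assumptions that are not in the documents: a three-group one-way ANOVA at alpha 0.05, with the effect size set so that 64 participants give 80% or 90% power.

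| Power at N = 64 | Power at N = 62 | Loss (percentage points) |
|---|---|---|
| 80% | 78.6% | 1.4 |
| 90% | 89.0% | 1.0 |

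**Chance of keeping at least 64 (illustration).** Assuming that each participant drops out independently with probability 0.20:

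| Enrolled | Probability of at least 64 completers |
|---|---|
| 78 | 39% |
| 80 | 57% |
| 81 | 65% |

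**The case against.** The strongest reply accepts the arithmetic and disputes its weight.

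- **The size is trivial.** The gap is 1.6 participants, the unrounded correct target is only 2 above 78, and the illustrated power loss is under 2 points. This stands: no conclusion of the trial plausibly turns on it, and it should not be reported as material underpowering.
- **The attrition rate is a forecast.** Under independent dropout the number of completers from 78 has a standard deviation of √(78 × 0.2 × 0.8) ≈ 3.5, so the shortfall is under half a standard deviation, and even 81 does not guarantee 64. This also stands, and it limits the claim to expected numbers. It does not make the sentence consistent: at the plan's own rate, falling short of 64 is the likelier outcome with 78.
- **The 64 is itself unexplained.** It has no stated basis and is not divisible by three, so a difference of 1.6 may be false precision. The missing basis is indeed the larger gap, but a separate one. The mismatch between 64, 20% and 78 holds whatever lies behind the 64.
- **Bilateral cases might make up the number.** Section 6 says that for participants with symptoms in both arms "the researcher will use each extremity as a separate unit", so the analysed units could exceed 62. But 64 and 78 are stated as participants, no number of bilateral cases is given, and two hands of one person are not independent. This does not rescue the figure.
- **Participants who leave early might still be analysed.** Section 11 does not say so. The planned change from baseline to end of study needs a final measurement, and no imputation is described.

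**Conclusion.** The concern holds. At the plan's own attrition rate, 78 enrolled gives an expected 62.4 completers, 1.6 fewer than the 64 said to be needed. The stated target covers 17.9% attrition, not 20%. The figure is consistent with multiplying by 1.2 where division by 0.8 was required.

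This conclusion uses only the figures in section 6 and reads attrition as a share of those enrolled. The power loss of about 1 to 1.5 points depends on the assumed one-way ANOVA and is given for scale only. The point is a small, definite arithmetic error that should be corrected; it does not threaten the trial's validity.

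**What to change.** Correct the sentence in section 6 in one of three ways:

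1. Keep 78 and state that it allows about 17.9% attrition while retaining 64. This costs one sentence and no added participants.
2. Keep 78 and 20%, state that about 62 completers are expected, and give the power for 62. No participants are added, but the authors must supply the inputs to their power analysis, which the document does not give.
3. Keep 64 and 20%, and raise the target to 81 (27 per group). This costs three more participants; the group size of 26 must change with it.

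Whichever is chosen, show the inflation formula. The counts are already worded as participants; because each arm of a bilateral case is handled as its own unit, it would help to add that they are not counts of hands.

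### Participants are randomised, but both hands of a bilateral participant count as separate units and no analysis allows for the pairing, so grip and pinch group tests can exceed their nominal error

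*Combined protocol and SAP*

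**What the plan says.** - **Randomisation** (section 8c, step 8): "Randomly assign participants using a random number generator, to one of three groups". The person is allocated, not the hand.
- **Bilateral participants** (section 6): "the researcher will use each extremity as a separate unit and apply corresponding intervention to both extremities". Section 8c, step 6, repeats the rule at the baseline visit: "If participant has symptoms in both extremities, the researcher will use each extremity as a separate unit".
- **Measurement** (section 9): "Data collection procedures on the affected extremity include psychometric assessments of pain". The singular leaves open what happens when both sides are affected.
- **Strength outcomes** (section 11): "repeated measures multi-factorial analysis of variance to analyze continuous data for the functional grip and pinch measurements", with an analysis of covariance, a change score from baseline to end of study, and "To compare groups post-hoc Bonferroni will be used".
- **Self-report scales** (section 11): Friedman's "Test will be used with the Numeric Pain Rating Scale, Visual Analogue Scale, and Boston Carpal Tunnel Questionnaire".
- **Sample size** (section 6): 64 participants, raised to 78 for 20% attrition, 26 per group. The count is of people.

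Section 11 contains no participant effect, hand-within-participant factor, clustered standard error, averaging over hands or choice of an index hand.

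**The concern.** Treatment differs only between participants. Two hands of one person share that person, the allocated treatment and the assessors, so their changes are likely to be positively correlated. They then carry less information than two hands from different people. Entering them as independent observations makes the between-group standard errors too small, the p-values too low and the confidence intervals too narrow. It also gives bilateral participants double weight in the group means.

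Bilateral participants are clearly expected. Section 5 does not exclude them, the rule for them is written twice, and section 6 recruits from occupations with repetitive hand use.

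At stake is the strength part of Objective 1, where the error runs towards a false claim of a difference between groups. The Friedman test compares visits rather than arms, so for the pain scales and the Boston questionnaire the problem is confined to the test of change over time within a group.

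**Working it through.** **1. Sample size.** 64 × 1.20 = 76.8, which rounds to 77 and then to 78 as the next multiple of three. This reproduces the plan's total. (Dividing by the retention rate instead gives 64 / 0.80 = 80.) The 64 itself cannot be reproduced, because no alpha, power, effect size or SD is given. Completers per arm are about 64 / 3 = 21.3, so 21 per arm (63 in all) is used below.

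**2. Assumptions.** The bilateral share b, the correlation ρ between the two hands' changes, and a two-sided alpha of 5% are all assumed, since the plan states none of them.

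**3. Design effect.** With m = 1 or 2 hands per participant:

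DE = 1 + (Σm² / Σm − 1) × ρ = 1 + 2bρ / (1 + b)

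The standard error is understated by 1 − 1/√DE. For b = 50% and ρ = 0.5, Σm²/Σm = 2.5/1.5 = 1.667, so DE = 1 + 0.667 × 0.5 = 1.333 and the understatement is 1 − 1/1.155 = 13.4%. The 63 participants supply 63 × 1.5 = 94.5 hands, worth 94.5 / 1.333 = 70.9 independent ones.

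**4. Simulated error with hands treated as independent and no true effect** (21 participants per arm):

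| b | ρ | DE | SE understated | Three-group F test on change | Bonferroni, familywise | Friedman over five visits, one group |
|---|---|---|---|---|---|---|
| 10% | 0.1 | 1.018 | 0.9% | 5.3% | – | – |
| 10% | 0.3 | 1.055 | 2.6% | 5.8% | 5.2% | 5.4% |
| 30% | 0.3 | 1.138 | 6.3% | 7.1% | 6.1% | 6.8% |
| 50% | 0.5 | 1.333 | 13.4% | 10.7% | 9.7% | 10.9% |
| 100% | 0.8 | 1.800 | 25.5% | 19.3% | 17.9% | 23.0% |

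The F-test column uses 100,000 runs per setting and the Friedman column 20,000. Without clustering, the Bonferroni familywise error is 4.7%. In the Friedman column ρ is the correlation between hands of their visit-to-visit deviations, which is not the same quantity as the correlation of changes.

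**5. Sensitivity to group size.** With 26 per arm (20,000 runs) the F-test error is 7.0% (b = 25%, ρ = 0.3), 10.9% (50%, 0.5) and 13.7% (100%, 0.5). Attrition therefore hardly matters. With b = 0 or ρ = 0 the error stays at about 5%.

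**6. Check of a remedy.** With one mean per participant, the F test rejects 4.8% to 5.1% of the time in the 100,000-run simulations, and the within-group Friedman test 4.4% to 4.7%.

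**The case against.** - **The rule may concern measurement and treatment only.** It appears in the recruitment and procedures sections, joined to the instruction to treat both sides, and section 11 names no unit of analysis. But nothing limits the rule to measurement, and nothing else in the plan says how two hands are analysed. The same correction is needed on either reading.
- **The multi-factorial model might carry hand as a within-participant factor.** The text does not say so, it conflicts with the stated rule, and such a factor does not directly fit a mix of one-hand and two-hand participants. The repeated-measures part covers visits within a unit, not the two hands of a person.
- **Bonferroni might protect.** It corrects for the number of comparisons, not for standard errors that are too small.
- **The size is unknown and may be trivial.** This stands. At 10% bilateral and correlation 0.1 the error is barely above nominal, and the 50%, 0.5 setting is illustrative. Section 9 gives test-retest reliability of about 0.80 for grip and pinch, so measurement error could be a large part of a short-term change. If that error is independent between hands, it lowers the correlation of changes and makes 0.8 an extreme. Shared effort or time of day could raise it.
- **The simulations are limited.** This also stands. They cover the change-score F test, pairwise comparisons and Friedman. The extension to the ANCOVA and repeated-measures ANOVA rests on the same reasoning but was not simulated, nor was the mixed model.

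**Conclusion.** The concern holds. Randomisation is by participant, the stated unit for bilateral participants is the hand, and no planned analysis reconciles the two. Whenever some participants are bilateral and their hands' changes are positively correlated, the between-group tests of grip and pinch reject too often.

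The direction is certain under those two conditions; the size is not. Over the assumed values the F-test error runs from about 5.3% to 19.3% against a nominal 5%, with about 10.7% (Bonferroni familywise about 9.7%) when half the participants are bilateral and the correlation is 0.5. Nothing in the plan caps the bilateral share or the correlation. For the three self-report scales the conclusion is narrower: only the within-group time test is affected. This should be corrected before the data are analysed.

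**What to change.** 1. **Sections 6 and 8c (step 6).** Keep the collection of data on both hands, but replace the separate-unit rule with a statement that the participant is the unit of randomisation and inference.
2. **Section 11, grip and pinch.** Analyse change from baseline with a random effect for participant, hands nested within participant, or with participant-clustered standard errors and a small-sample correction. If all visits are modelled jointly, include participant-by-visit effects as well as participant and hand-within-participant effects. A participant random intercept alone cancels out of change from baseline and leaves the correlation of the two hands' changes unmodelled. The Bonferroni comparisons should come from this model.
3. **Section 11, rank tests.** Use one prespecified value per participant and visit, for example the mean of the two hands. The same reduction is a simple fallback for grip and pinch, and is the version whose error was checked above.

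The sample-size text needs no change here, since 64 and 78 already count participants.

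**Cost.** Analysis wording only, with no new data or visits. Relative to the hand-as-independent analysis, standard errors for grip and pinch widen by √DE − 1: about 1% at the low end (√1.018), 15% at 50% bilateral and correlation 0.5 (√1.333), and 34% at the top (√1.800). That is their correct size under those assumptions.
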